**Table 3: PLX3397 Dose Modification Guidelines for Treatment-Related Toxicities, Excluding Liver Function**

All Drug-Related Toxicities	Frequency	When to Hold or Stop	When to Restart and Restart Dose (See Table 2 for dose levels.)
Grade 3 or 4 neutropenia	1st Appearance	Interrupt until ANC recovers to $\geq 1 \times 10^9/L$ ; growth factor support permitted	If recovered to ANC $\geq 1 \times 10^9/L$ in $\leq 7$ days, resume at same dose.
			If not recovered to ANC $\geq 1 \times 10^9/L$ after 7 days, reduce dose by 1 dose level.
	2nd Appearance	Interrupt until ANC recovers to $\geq 1 \times 10^9/L$ ; growth factor support permitted	If recovered to ANC $\geq 1 \times 10^9/L$ in $\leq 7$ days, reduce dose by 1 dose level.
			If not recovered to ANC $\geq 1 \times 10^9/L$ after 7 days, reduce dose by 2 dose levels.
3rd Appearance	Interrupt until ANC recovers to $\geq 1 \times 10^9/L$ ; growth factor support permitted	If recovered to ANC $\geq 1 \times 10^9/L$ in $\leq 7$ days, reduce dose by 1 dose level.	
		If not recovered to ANC $\geq 1 \times 10^9/L$ after 7 days, discontinue permanently.	
4th Appearance	Discontinue permanently; growth factor support permitted	N/A	
Grade 3 or 4 febrile neutropenia	1st Appearance	Interrupt until ANC and fever recover; provide growth factor support	If recovered to ANC $\geq 1 \times 10^9/L$ and $T \leq 38^\circ C$ in $\leq 7$ days, reduce dose by 1 dose level.
			If not recovered to ANC $\geq 1 \times 10^9/L$ after 7 days, discontinue permanently.
	2nd Appearance	Interrupt until ANC and fever recover; provide growth factor support	If recovered to ANC $\geq 1 \times 10^9/L$ and $T \leq 38^\circ C$ , reduce dose by an additional 1 dose level.
If not recovered to ANC $\geq 1 \times 10^9/L$ after 7 days, discontinue permanently.			
3rd Appearance	Discontinue permanently; provide growth factor support	N/A	
Grade 4 thrombocytopenia	1st Appearance	Interrupt until PLT $\geq 75 \times 10^9/L$	If recovered to PLT $\geq 75 \times 10^9/L$ $\leq 7$ days, resume at same dose.
			If not recovered to PLT $\geq 75 \times 10^9/L$ after 7 days, reduce dose by 1 dose level.
	2nd Appearance	Interrupt until PLT $\geq 75 \times 10^9/L$	If recovered to PLT $\geq 75 \times 10^9/L$ in $\leq 7$ days, reduce dose by 1 dose level.
			If not recovered to PLT $\geq 75 \times 10^9/L$ after 7 days, reduce dose by 2 dose levels.
3rd Appearance	Interrupt until PLT $\geq 75 \times 10^9/L$	If recovered to PLT $\geq 75 \times 10^9/L$ in $\leq 7$ days, reduce dose by 1 dose level.	
		If not recovered to PLT $\geq 75 \times 10^9/L$ after 7 days, discontinue permanently.	
4th Appearance	Discontinue permanently	N/A	

All Drug-Related Toxicities	Frequency	When to Hold or Stop	When to Restart and Restart Dose (See Table 2 for dose levels.)
Non-Hematologic Grade 3 (excluding transaminase increases)	1st Appearance a	Interrupt until resolved (Grade 0 -1); start symptomatic treatment if possible	If recovered ≤5 days, resume at same dose. If symptoms persist for >5 days despite supportive management, reduce by 1 dose level. b
	2nd Appearance	Interrupt until resolved (Grade 0-1); start symptomatic treatment if possible	If recovered ≤5 days, reduce dose by 1 dose level. If symptoms persist for >5 days despite supportive management, discontinue permanently.
	3rd Appearance	Discontinue permanently; start symptomatic treatment if possible	N/A
Non-Hematologic Grade 4 (excluding transaminase increases)	1st Appearance	Interrupt until resolved (Grade 0-1); start symptomatic treatment if possible	If recovered <5 days, reduce by 1 dose level. If symptoms persist for ≥5 days despite supportive management, discontinue permanently.
	2nd Appearance	Discontinue permanently; start symptomatic treatment if possible	N/A

ANC = absolute neutrophil count; INR = international normalized ratio; N/A = not applicable; PLT = platelet; T = temperature; ULN = upper limit of normal

a Except for cases of Grade 3 emesis.

b Except in cases of Grade 3 symptomatic rash.

Dose interruptions for Grade 2 non-hematologic toxicity for up to 1 week can be implemented at the discretion of the treating physician to manage intolerable or clinically significant toxicity. No dose reduction is required when resuming treatment.

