### 13.13 Dose Levels for the Phase 1b Portion

#### 13.13.1 Dose Escalation

A total of approximately 7 patients will be enrolled in each dose level (see [Table 2](#)). The starting dose level of PLX3397 will be 800 mg/day administered 7 days/week (Cohort 1).

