**Table 2: PLX3397 Dosing Cohorts**

Cohort	Combination PLX3397/RT/TMZ		Adjuvant PLX3397/TMZ	
	PLX3397 Dose	PLX3397 Schedule	PLX3397 Dose	PLX3397 Schedule
-2	600 mg/day	5 days/week (M-F) b	800 mg/day b	7 days/week
-1	600 mg/day	7 days/week a	600 mg/day a 800 mg/day b	7 days/week
1	800 mg/day	7 days/week a 5 days/week (M-F) b	1000 mg/day b	7 days/week
2	1000 mg/day	5 days/week (M-F) b	1200 mg/day b	7 days/week

a Amendment 1.

b Amendment 2.

Study drug will be administered orally using a capsule formulation (200 mg per capsule). The total daily dose of PLX3397 will be divided and administered BID. For an uneven number of capsules, the larger dose will be administered in the morning.

For combination PLX3397/RT/TMZ PLX3397 treatment, dose escalation to the next highest cohort may occur after all patients have completed the 11-week DLT-observation period (i.e., 1-week PLX3397 monotherapy; 6-week PLX3397/RT/TMZ combination therapy; 4-week recovery). For adjuvant PLX3397/TMZ PLX3397 treatment, dose escalation to the next highest cohort may occur after all patients have completed an 8-week DLT-observation period (i.e.,

2 cycles of adjuvant treatment). For patients participating in Phase 1b, intra and inter patient dose escalation to a higher dose level/schedule will be permitted after that dose level/schedule has been established to be safe.

Prior to dose escalation, safety data will be collated and reviewed by the Sponsor and study sites by teleconference. A dose level will be considered unacceptable if 2 or more patients of the 6 eligible patients experience a DLT (see below). Should all 7 patients in the Cohort be analyzable for adverse events, only the first 6 will be considered in the determination of DLTs. A patient who misses more than 7 days of PLX3397 administration during the 7-week dosing period of Cycle 1 (4 weeks) and Cycle 2 (3 weeks) for reasons other than having had a DLT will be replaced. If 2 or more patients in a Cohort experience a DLT, no patients in the Cohort will be replaced.

If 2 or more of the first 6 patients in Cohort -2 (600 mg/day of PLX3397; 5 days/week [M-F]) experience a protocol-defined DLT, the combination will be considered too toxic and the study will be discontinued.

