Dose reduction/interruption guidelines for hematologic and nonhematologic treatment-related TEAEs are based on severity. Dose interruptions can be implemented at the discretion of the treating Investigator to manage intolerable or clinically significant toxicity. If a dose interruption is required, study assessments should be performed as scheduled, irrespective of the study drug delay, with the exception of PK assessments, which should be deferred until treatment is resumed. Interruptions due to toxicity lasting >14 days require treatment discontinuation unless the medical monitor approves continuation.

Dose reductions of temozolomide should be made according to the prescribing information noted in [Attachment 4](#) and also summarized in [Section 16](#).

Below are guidelines for dosage modification for PLX3397-related toxicities as well as guidelines for their management. Dose reductions should occur in increments of 200 mg/day, depending on the toxicity grade, as noted in [Table 3](#), [Table 4](#), and [Table 5](#). As the capsules are provided in 200 mg strengths, dose reduction should occur by a reduction of one capsule from either the morning or evening dose.

Up to 5 days of treatment interruption are permitted for any reason. Interruptions of 6 to 7 treatment days will be considered an acceptable protocol deviation. For interruptions of 8 days or greater, continuation of patients in the study should be discussed with the medical monitor.

Temozolomide dose reduction should be made according to the prescribing information noted in [Attachment 4](#) and also summarized in [Section 16](#).

These parameters are only a guide and are not intended to supersede the clinical judgment of the treating physician. All adjustments should be made in consultation with the Medical Monitor.

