## **21.0 STATISTICAL ANALYSIS**

### **21.1 General Statistical Considerations**

#### **21.1.1 Phase 1b Portion**

The objective of the Phase 1b portion of this study is to determine the recommended Phase 2 dose (RP2D) of PLX3397 when combined with concurrent radiation therapy and temozolomide. Two expected dose levels are specified for testing, with one or more lower doses to be evaluated if the starting dose of 800 mg/day is above the MTD. For each dose level, 7 patients will be accrued to assure that there will be 6 patients eligible for evaluation of toxicity. A patient registered to the study who is found retrospectively not to meet the study eligibility criteria, who does not receive any PLX3397, or who is considered non-evaluable during the toxicity evaluation period for reasons not related to study drug will be excluded from evaluation of DLT and replaced.

Patient accrual will be suspended after each dose cohort is enrolled until there is sufficient information collected to make a decision relative to dose escalation. A dose level for PLX3397 will be considered acceptable if no more than 2 patients of the 6 eligible patients experience a DLT. Should all 7 patients be analyzable for adverse events, only the first 6 will be considered in the determination of DLTs. If the current level is considered acceptable, then dose escalation will occur and the protocol will be reopened. Otherwise, the preceding acceptable dose level will be declared the MTD. The Sponsor, together with the study investigators, will evaluate the safety of each cohort prior to dose escalation.

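### Table 3 counts PLX3397 reductions in Table 2 dose levels, which do not match the 200 mg/day step in the text and at some levels give no reduction

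*Combined protocol and SAP*

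**What the plan says.** Two descriptions of a PLX3397 reduction sit side by side in the protocol.

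**By dose level.** Table 3 covers drug-related toxicity other than liver function. Its last column is headed "When to Restart and Restart Dose (See Table 2 for dose levels". Entries call for one level or, for a second unrecovered Grade 3-4 neutropenia, "after 7 days, reduce dose by 2 dose levels"; Grade 4 thrombocytopenia follows the same pattern. Section 13.13.1 treats a dose level as a row of Table 2: "A total of approximately 7 patients will be enrolled in each dose level", with a reference to that table. Section 13.14.1 also sends the reader to 13.13.1 for dose reductions.

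**By 200 mg/day.** Section 13.14.2 says "Dose reductions should occur in increments of 200 mg/day, depending on the toxicity grade" and adds that this is done by removing one capsule from the morning or the evening dose. Section 13.14.1 gives the same increment, and Table 4 (liver abnormalities) makes each reduction one 200 mg capsule.

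**Table 2** has four rows (-2, -1, 1, 2), each with a combination-period and an adjuvant-period dose, and marks entries a (Amendment 1) or b (Amendment 2). Row -2 reads "600 mg/day 5 days/week (M-F) b 800 mg/day b 7 days/week". The adjuvant dose in row -1 reads "600 mg/day a 800 mg/day b".

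Section 13.14.2 also says that the parameters are guidance, do not override clinical judgment, and are applied in consultation with the Medical Monitor.

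**The concern.** A reduction rule needs a ladder on which each rung is lower than the one above. Table 2 was built to list escalation cohorts: it mixes two schedules and two amendments in four rows, and two neighbouring rows share a daily dose. A site that follows Table 3 to Table 2 can reach a different restart dose from a site that follows the one-capsule wording, for the same patient and event. At some rows the first site finds no lower dose.

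Table 3 governs restart after Grade 3-4 neutropenia, febrile neutropenia, Grade 4 thrombocytopenia and Grade 3-4 non-hematologic toxicity. If the rule has two meanings, sites will manage these events differently, delivered dose after toxicity will vary for reasons unrelated to the patient, and monitoring cannot say whether a given restart was a protocol deviation.

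**Working it through.** **Inputs.** All doses are from Table 2, in mg/day. The step is 200 mg/day (13.14.1, 13.14.2). For the comparison I assume that one level is meant to equal one 200 mg step, so two levels should be 400 mg/day.

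**Adjuvant period, Amendment 2 entries (all 7 days/week)**

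| Start row, dose | 1 row down | Dose - 200 | 2 rows down | Dose - 400 |
|---|---|---|---|---|
| 2, 1200 | 1000 | 1000 | 800 | 800 |
| 1, 1000 | 800 | 800 | 800 | 600 |
| -1, 800 | 800 | 600 | none listed | 400 |
| -2, 800 | none listed | 600 | none listed | 400 |

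The rules agree from row 2. From row 1 a two-level reduction is 1000 - 800 = 200 mg/day, the same as a one-level reduction. From row -1 a one-level reduction is 800 - 800 = 0. From row -2 there is nowhere to go.

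Row -1 also carries the Amendment 1 adjuvant dose of 600. Read from that entry, one row down is 600 to 800, an increase of 200 mg/day. This step crosses amendments.

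**Combination period**

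| Start row, dose | 1 row down | Dose - 200 | 2 rows down | Dose - 400 |
|---|---|---|---|---|
| 2, 1000 (5-day) | 800 (7- or 5-day) | 800 | 600 (7-day) | 600 |
| 1, 800 (7- or 5-day) | 600 (7-day) | 600 | 600 (5-day) | 400 |
| -1, 600 (7-day) | 600 (5-day) | 400 | none listed | 200 |
| -2, 600 (5-day) | none listed | 400 | none listed | 200 |

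In mg/day the column from the bottom up is 600, 600, 800, 1000. There is one tie and no reversal; at the tie only the days per week change, from 7 to 5.

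**Does the capsule rule work alone?** Take 600 mg/day, a first unrecovered neutropenia (1 level) and then a second (2 levels).
- If reductions accumulate: 600 - 200 = 400, then 400 - 400 = 0 mg/day.
- If the second is counted from the starting dose: 600 - 400 = 200 mg/day. That is a single capsule, while 14.1 has the daily dose divided in two.

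Table 3 does not say which reading applies, and in both cases its instruction is still to reduce.

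**Order of cohorts.** Section 10.2 counts five cohorts, two from Amendment 1 and three from Amendment 2; Table 2 shows them in four rows, with Cohort 1 covering a 7-day and a 5-day schedule. Section 13.13.1 escalates to the next highest cohort without setting out how 5-day and 7-day cohorts are ordered relative to each other.

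**The case against.** The step size is stated, and repeatedly. Section 13.14.2 presents Table 3 as carrying out 200 mg/day steps, and Table 3's own verb is to reduce, so restarting at an equal or higher dose would go against its instruction. The guidance-only clause and Medical Monitor consultation add protection. This makes a wrong restart less likely. It does not say which rule prevails, and the Medical Monitor reads the same conflicting text.

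Splitting Table 2 by amendment also helps. The footnoted combination entries match the counts in 10.2. If row -1 is skipped for Amendment 2, the steps are 1000/800/600 (combination) and 1200/1000/800 (adjuvant), 200 mg/day each. But row -1 has its own Amendment 2 adjuvant entry of 800, no section says to skip it, and the skip leaves nothing below the last rung.

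The zero-dose sequence depends on a cumulative reading. The febrile neutropenia row speaks of an additional level and the neutropenia row does not, so counting from the starting dose is equally possible. The sequence needs two unrecovered events, and toxicity interruptions over 14 days require discontinuation unless the Medical Monitor approves continuation. These limits stand.

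Three stronger inferences are not supported:
- That Table 3 generally raises the dose. The only mg/day increase takes an Amendment 1 entry to an Amendment 2 entry.
- That the combination column is out of order by weekly dose. The protocol states and reduces doses in mg/day and never ranks cohorts by weekly total.
- That the MTD or RP2D cannot be identified. The rule in 21.1.1, "Otherwise, the preceding acceptable dose level will be declared the MTD", does not cite Table 2 and can mean the last level tested and found acceptable.

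**Conclusion.** The inconsistency is real. As printed, Table 3 read through Table 2 disagrees with the 200 mg/day rule for some listed starting doses. Within Amendment 2's adjuvant entries alone, one level down from row -1 changes nothing, where the text requires 200 mg/day; two levels down from row 1 gives 200 mg/day, where two 200 mg steps give 400. In the combination period, one level down from row -1 keeps 600 mg/day and changes only the schedule. No level is listed below row -2, and no text covers a patient with no lower step.

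The size is limited: from row 2 the two rules give the same mg/day for one and two levels on Amendment 2 adjuvant entries and in the combination column. The comparison rests on reading a dose level as a Table 2 row, as 13.13.1 and the Table 3 header do, and on one level being meant as one 200 mg step. The undefined order of the 5-day and 7-day cohorts is secondary. It is a gap in the escalation wording and does not show that the Phase 1b objective fails.

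**What to change.** The sponsor should reconcile Table 2, Table 3, 13.13.1, 13.14.1 and 13.14.2 so that:

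1. A reduction by one dose level has a single meaning, the same in text and tables.
2. For every listed starting dose, separately for the combination and adjuvant periods, each step is lower than the one before and can be given with 200 mg capsules on the stated schedule.
3. Table 3 says whether a later reduction is counted from the current or the starting dose.
4. The text says what applies when no lower step exists.
5. The 5-day and 7-day cohorts are listed in a stated order for escalation, with the two Cohort 1 schedules named separately.

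In the same edit, the description of Cohort -2 as 400 mg/day (synopsis stopping rules and 13.16) needs reconciling with 600 mg/day in Table 2, and 13.14.2's references to Tables 3.1 to 3.3 need correcting, since no tables carry those numbers.

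Which rule governs and which doses appear are the sponsor's decisions; simply deleting the pointer to Table 2 would make that choice by default. The cost is one reduction table and a few sentences in an amendment, with no added patients or procedures.

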**Table 4: Dose Modification Guidelines for Liver Function Abnormalities**

Toxicity Grade CTCAE v4.0	Initial Action	Outcome	Action
ALT or AST Grade 2 (>3-5 × ULN); No increase in bilirubin a	Re-check ALT and AST immediately Hold study drug Monitor weekly b Check for changes to medications and for symptoms	Resolution to Grade 0–1 or baseline (no bilirubin increase)	Restart on resolution Grade 0–1 or baseline at 1 dose lower (reduce by one 200 mg capsule)
Grade 3 ALT or AST increase (>5-20 × ULN); No increase in bilirubin a	Re-check ALT and AST immediately Hold study drug Monitor 2x/week b Check for changes to medications and for symptoms	Resolution to Grade 0–1 or baseline (no bilirubin increase) within 14 days	Restart on resolution to Grade 0–1 or baseline at 1 dose lower (reduce by one 200 mg capsule)
		ALT and AST not decreasing within 14 days of holding study drug	Proceed to liver evaluation as outlined in Table 5 . Restart only on resolution to Grade 0-1/baseline at 1 dose lower (reduce by one 200 mg capsule); For max AST or ALT >8 × ULN, consult with medical monitor prior to re-start
Grade 4 ALT or AST (>20 × ULN)	Discontinue treatment Monitor 2x/week until resolution to Grade 2 Follow-up until resolution Grade 0–1 or baseline Check for changes to medications and for symptoms	All outcomes	Discontinue treatment; Proceed to liver evaluation as outlined in Table 5 . If clear confirmed alternate cause, restart on resolution to Grade 0–1 or baseline at 1 dose lower (reduce by one 200 mg capsule)
Any grade ALT or AST increase a with any bilirubin increase or signs of hypersensitivity	Discontinue treatment Monitor 2x/week until resolution to Grade 2 Follow-up until resolution Grade 0-1 or baseline Check for changes to medications and for symptoms	All outcomes	Discontinue treatment; Proceed to liver evaluation as outlined in Table 5 . If clear confirmed alternate cause, restart on resolution to Grade 0–1 or baseline at 1 dose lower (reduce by one 200 mg capsule)

ALT = alanine aminotransferase; AST = aspartate aminotransferase;

CTCAE = Common Terminology Criteria for Adverse Events; ULN = upper limit of normal

a An increase in bilirubin is defined as all of the following: total bilirubin >ULN, total bilirubin >20% above baseline, and direct bilirubin is >ULN. If all of these conditions are met, then bilirubin is considered increased and should be immediately re-checked. Pexidartinib treatment should be immediately discontinued for increased bilirubin unless and until there is a clear, confirmed alternate cause.

b If ALT, AST, or bilirubin worsens during the monitoring period, follow the applicable guidance for the worst toxicity grade.

**Table 5: Additional Liver Evaluation**

Evaluation	Comments
Increase frequency of testing liver chemistries to twice per week, including INR, and continue until liver chemistries have stabilized, and then reduce to weekly until liver chemistries return to normal or baseline.	Investigational treatment may be started after liver function tests recover to Grade 0 to 1 or baseline level, and in consultation with Medical Monitor.
Detailed history focusing on medications and substances used: alcohol, change in medication dosages, new medications added, attention to use of acetaminophen, OTC medication use, and recreational drug use. Check for change in diet or use of dietary supplements, with particular attention to dose and duration of any herbal product.	Suspect medications will be discontinued or substituted for if possible.
Detailed medical history and physical examination seeking new abnormalities.	Evaluate abnormalities found.
Full serological evaluation for hepatitis A, B, C, and E (IgG and IgM). Check for autoimmune hepatitis with serological laboratory studies.	If viral hepatitis or autoimmune hepatitis suggested, have patient evaluated by hepatologist.
Liver ultrasound performed to evaluate liver and biliary tree.	Evaluate any abnormalities found.
Check history for exposure to chemical agents.	Remove chemical exposure and have patient seen by hepatologist.
Obtain hepatology consult if liver function continues to rise beyond 14 days.	Contact Medical Monitor.
We request that cases be discussed with the Medical Monitor as defined in the protocol whenever investigational product is being held for liver function test abnormality.	

Ig = Immunoglobulin; INR = international normalized ratio; OTC = over-the-counter

For suspected cases of cholestatic liver injury (eg, aminotransferase increase concurrent with hyperbilirubinemia, or liver biopsy suggesting cholestasis and/or ductopenia), patients will be followed to assess long-term outcome. Additional diagnostic and follow-up procedures might be implemented as appropriate to fully assess the event.

### **13.15 Discontinuation of Treatment, Patient Withdrawal, and Replacement**

The reasons a patient may discontinue or be withdrawn from the study include, but are not limited to, adverse event, disease progression, patient request, investigator decision, protocol violation, patient noncompliance, and study termination by the Sponsor. When a patient discontinues or is withdrawn, the investigator will notify the Sponsor and should perform the procedures indicated in the End of Rx column in the trial flow chart within 30 days after discontinuation of study drug and prior to initiation of any therapy. After discontinuation of study drug, patients and/or their families will continue to be monitored by telephone every 6 months for OS.

Patients withdrawn from the study for reasons other than toxicity or disease progression (e.g. protocol violation or noncompliance) may be replaced at the discretion of the medical monitor and the investigator. Study drug administration may be discontinued for an adverse event or at the discretion of the investigator.

